Participant selection: Following IRB approval, we will recruit 24 MCI participants and 24 healthy, age-matched controls through e-mail notices, posters, and word-of-mouth. MPOD will be assessed at the recruitment stage for all subjects to determine their initial eligibility, which will require subjects to fit into one of 2 distinct groups (low: MPOD < 0.3, high: MPOD > 0.5). **Eligible participants will be MCI or mild AD patients who are 55 years and older.** We will work with our physician collaborators in the area (who are currently working with the PIs in 3 other R01s) to perform the pre-selection diagnosis according to the following **pre-selection criteria:** Participants must be diagnosed by their physician with amnestic MCI or mild AD. Subjects in the control group will have normal cognition. Study participants who meet the following inclusion and exclusion will discuss informed consent for study participation: **Inclusion criteria:** Those taking antidepressants will be included, but type of medicine and dosage intake will be monitored. There will be no exclusions based gender, race, and ethnicity. Participants must also not meet the following **Exclusion criteria:** Presence of another brain disease that fully explains the dementia (extensive brain vascular disease, Parkinson's disease, dementia with Lewy bodies, traumatic brain injury, or multiple sclerosis); residence in a skilled nursing facility or long-term care; indication for psychiatric hospitalization or acute suicidality in the opinion of the physician; major organ failure (e.g., kidney failure); or uncontrolled generalized disorders such as hypertension or diabetes. Exclusion criteria will also extend to obstructing cataracts, macular degeneration, and blindness. Those taking over-the-counter melatonin, prescription sleep medication or beta blockers will be excluded. We will review the participants' ophthalmologic tests during selection and exclude those who have undergone

[figure not shown]

Fig. 2. Correlation between MPOD and melatonin suppression showing pooled data from a series of within-subjects nighttime studies. Each yellow diamond corresponds to suppression data for an individual subject. The black line corresponds to the best fit linear regression model. All subjects underwent a 1-h exposure to white light sources with CCTs ranging

[figure not shown]

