Fig. 3. Relative spectral power distributions of potential narrowband blue light source ($\lambda_{\text{max}} = 451 \text{ nm}$) and green light source ($\lambda_{\text{max}} = 522 \text{ nm}$). Also shown is the relative spectral absorbance of the macular pigment, adapted

cataract surgery and received an intraocular lens coated with ultraviolet- and blue-blocking filters (400-440/440-500 nm). Those with a history of severe photosensitivity dermatitis, severe progressive retinal disease (e.g., macular degeneration), or a permanently dilated pupil (e.g., after certain types of cataract surgery) will also be excluded. Subjects will also be required to maintain a regular sleep schedule (bedtimes no later than 23:00 and wake times no later than 08:00) starting 2 weeks prior to the experimental sessions and continuing throughout the experiment's duration. The experimenters will run the dim-light control condition first, and any subjects who present low nighttime (i.e., at 24:00) melatonin levels will be excluded from the study. This study will conform to the Code of Federal Regulations (CFR) document Protection of Human Subjects, 45 CFR 46, ⁶⁷ and International Ethical Standards. ⁶⁸

Experimental conditions: In addition to a dim-light control condition, participants will be exposed to 2 narrowband sources: blue light ($\lambda_{\max} = 451$ nm) and green light ($\lambda_{\max} = 522$ nm) (Fig. 3), presented in 4 interventions. The 2 interventions for each narrowband source, designated on-axis and off-axis, will have distinct lighting distribution patterns but calibrated to deliver the same targeted levels of circadian light (CL_A) and circadian stimulus (CS) at the eye. ^{60,69} The 4 interventions will target a CS = 0.40 (≈ 27 lux for blue light, ≈ 250 lux for green light) at the participants' eyes and the dim light control will target a CS < 0.1 (< 5 lux of 2700 K light) at the eyes. The 4 lighting conditions will be counter-balanced across all the participants. Over the course of the study, spectral irradiance measurements for the 2 narrowband sources will be performed using a spectrometer (Model USB650, Ocean Optics, Winter Park, FL, USA).

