Sample Size and Estimated Power. The study will have enough power to detect treatment differences. Previous work by our lab⁷⁴ provides measures of variability for our primary outcome measures (melatonin suppression and questionnaires). In particular, a prior within subjects' study⁷⁴ involving effects of white light on nighttime melatonin suppression have shown that a sample size of 12 or more participants is enough to detect statistically significant ($\alpha = 0.05$) difference in suppression ($\approx 14\%$) for a large effect (Cohen's $d > 0.5$) at a statistical power $\approx 95\%$. A sample size of 19 subjects (24 subjects, 20% attrition) for each group, therefore, should be sufficient for the detection of significant differences in melatonin suppression.

Data and Statistical Analyses

Anticipated Outcomes. Our hypothesis is that greater melatonin suppression will be observed for the on-axis interventions, compared to the off-axis interventions, due to 2 reasons: (1) the greater density of cone photoreceptors in central retina (which will account for about 12% melatonin suppression difference according to CS model calculations⁷⁰) and (2) the *Stiles-Crawford* effect, which suggests that the most effective optical rays incident on the retina are along the foveal axis. Overall, we also expect to see greater melatonin suppression for the low MPOD group compared to the high MPOD group, as higher MPOD means greater attenuation of the photic stimulus. We further hypothesize a significant interaction between the effect of MPOD and light source spectrum, as the yellow macular pigment preferentially filters out short-wavelength radiation, and hence should only attenuate the blue light stimulus. In other words, for high MPOD subjects, we expect to see greater melatonin suppression following exposure to the green light as compared to the blue light exposure. Lastly, we expect to observe a significant interaction between the effect of MPOD and lighting distribution, as since the yellow macular pigment is located primarily in the central retina, the off-axis dose should not be affected by it. Finally, we hypothesize that lower MPOD scores will be associated with lower cognition.

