Overall Analyses will include (1) evaluation to determine data quality, (2) creation of constructed variables and determination of variable distributions, (3) applying tests of parametric statistical assumptions wherever appropriate, (4) preliminary (generally bivariate) testing of hypotheses, (5) consideration of potential covariates to build into the statistical models to increase the probability of detecting treatment effects if they exist, and (6) development and elaboration of multivariate models. SPSS software (V25, IBM, Armonk, NY, USA) will be used for all statistical analyses (significance, $p < 0.05$). [name] will perform all statistical analyses and work with Drs. [name] and [name] on statistical analyses.

Aims 1, 2: In order to evaluate outcomes of the intervention, we will first determine the melatonin suppression for each condition by comparing melatonin levels collected during the dim-light control week to those at the same time in the experimental conditions' weeks. We will then perform a mixed-model analysis of variance (ANOVA), with lighting distribution (on-axis vs. off-axis) and spectrum (blue light vs. green light) serving as the within-subjects factors, and MPOD group (high MPOD > 0.5 vs. low MPOD < 0.3) and cognitive status (MoCA scores) (healthy vs. MCI participants) serving as the between-subjects factors. Mixed model analyses allow for different numbers of observations for different subjects (e.g. if there are dropouts). As sample size and its associated degrees of freedom allow, we will also adjust for covariates that may be associated with outcome measures, such as retinal illuminance, gender, season and any medication load. Within the limits of the sample, we will explore treatment-covariate interactions for each participant-level covariate. If strong interactions are observed, it will suggest that a future study could possibly be stratified on the given factor. To further assess the impact of MPOD on individual light sensitivity, a Pearson correlation coefficient will be calculated between melatonin suppression and MPOD values recorded across MCI patients and healthy older adults. We hypothesize a negative correlation, wherein higher MPOD values will be associated with lower suppression.

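### Lighting conditions are counter-balanced over sessions, but the Aims 1-2 model has no session term, so session-to-session drift stays in the residual and makes the on/off test conservative

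*Combined protocol and SAP*

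**What the plan says.** **Design.** Under Experimental conditions: "The 4 lighting conditions will be counter-balanced across all the participants". The scheme (type of square, number of orders, how conditions are labelled) is not given. The reference night is outside the counter-balancing; under Participant selection, "The experimenters will run the dim-light control condition first". The Aims 1, 2 text compares "melatonin levels collected during the dim-light control week" with levels at the same clock time in the experimental weeks, so visit order is also a time axis of several weeks.

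**Model.** Under Data and Statistical Analyses, Aims 1, 2, the analysis is a mixed-model ANOVA "with lighting distribution (on-axis vs. off-axis) and spectrum (blue light vs. green light) serving as the within-subjects factors", with MPOD group and cognitive status between subjects. Provided that the sample proves large enough, the plan adds: "we will also adjust for covariates that may be associated with outcome measures, such as retinal illuminance, gender, season and any medication load". No session, period or sequence term is named anywhere.

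**Attrition.** Under Participant selection, "we will recruit 24 MCI participants and 24 healthy, age-matched controls". The sample-size section plans on "A sample size of 19 subjects (24 subjects, 20% attrition) for each group". The analysis section adds: "Mixed model analyses allow for different numbers of observations for different subjects (e.g. if there are dropouts").

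**The concern.** Counter-balancing keeps drift out of the average on/off contrast while the orders are equally represented. It does not take drift out of the residual; only a model term does that. If suppression changes with visit number, for example through habituation to the laboratory, each participant's four values vary for a reason the model does not know about, and that variation is counted as error. The SE is then overstated and power is lost. Planned attrition also means that the orders will not be equally represented at the end: 19 completers per group cannot fill four sequences equally. What is at stake is mainly efficiency, and secondarily robustness to drift in the realised sample.

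**Working it through.** **Inputs from the documents.** Enrolment is 24 + 24 = 48. With 20% attrition, 24 × 0.8 = 19.2, so the plan's 19 per group reproduces, giving 38 completers. Four active sessions. Expected on/off difference about 12 points (Anticipated Outcomes).

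**Assumptions, not in the documents.** Within-subject SD of a single suppression value σ = 10 points; linear drift D = 0, 2, 3 or 5 points per session.

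**1. Pooled residual.** Centred session positions are −1.5, −0.5, 0.5, 1.5, with sum of squares 5. Drift adds about 5D² to each participant's within-subject sum of squares, spread over 3 degrees of freedom. The SE is therefore inflated by

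√(1 + (5/3)D²/σ²)

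| D | (5/3)D² | SE ratio |
|---|---|---|
| 0 | 0 | 1.00 |
| 2 | 6.67 | √1.067 = 1.033 |
| 3 | 15 | √1.15 = 1.072 |
| 5 | 41.7 | √1.417 = 1.190 |

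Simulation with 48 enrolled and 38 completing gives 0.997, 1.03, 1.07 and 1.19 (SE without session divided by SE with session). The first figure is the cost of the term when there is no drift: under 0.5%.

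**2. Subject-by-distribution error.** A mixed ANOVA may instead test distribution against its own interaction with subject. Each participant's contrast (mean of two on-axis values minus mean of two off-axis values) has variance σ²/2 + σ²/2 = σ² = 100. Drift adds vD², where v is the variance over sequences of the on-minus-off difference in mean position:

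| Scheme | v | SE ratio at D = 5 |
|---|---|---|
| Williams square, one labelling | 0 | 1.00 |
| Cyclic square, on-axis conditions two steps apart in the cycle | 1 | √1.25 = 1.12 |
| All 24 orders | 1.67 | √1.417 = 1.19 |
| Cyclic square, on-axis conditions next to each other in the cycle | 2 | √1.50 = 1.22 |
| Williams square, other labellings | 2.5 | √1.625 = 1.27 |

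So at D = 5 the inflation is anywhere from 0% to about 27%.

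**3. Random dropout.** Take all 24 orders, each used twice, with 38 of 48 completing at random. The mean shift in the on/off estimate is zero. Its SD is D × √[(1.67 × 48/47)/38 × (1 − 38/48)] = 0.097D, or 0.19 points at D = 2 and 0.48 at D = 5. If all 10 losses fell on the least favourable orders, the shift would be (8 × 2 + 2 × 1)/38 = 0.47 times D.

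**4. Type I error at D = 5, pooled residual.** SE without drift: 10/√38 = 1.62. Reported SE: 1.62 × 1.19 = 1.93. Actual spread: √(1.62² + 0.48²) = 1.69. The effective critical value is 1.96 × 1.93/1.69 = 2.24, so the actual two-sided error is about 2.5% (2.6% in simulation). The test is conservative, not liberal.

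**5. With session in the model.** This simulation used a different assumed SD (12.2 points for a single paired difference, so about 8.6 per value) and random dropout. The SE of the on/off contrast was 1.35 at every drift with session, against 1.41 (D = 2) and 1.68 (D = 5) without it. Power for an illustrative 5-point effect was 0.96 with session at either drift, against 0.95 (D = 2) and 0.89 (D = 5) without. With an assumed dropout of 10% after an on-axis session and 2% after an off-axis one, mean bias without session was +0.12 (D = 2) and +0.43 (D = 5); with session it was about zero.

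**The case against.** **The drift is hypothetical.** The documents give no drift. Five points per session is 15 points from session 1 to session 4, more than the expected 12-point effect; at 2 points the loss is about 3% in SE. This stands, and is why the size is given as a range that includes zero.

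**The plan already limits drift.** A regular sleep schedule is required and checked by diary and actigraphy, season is a named covariate, and the dim-light night comes first, so a first-night effect falls on the control; a shift common to all four conditions cancels in the on/off contrast. This lowers the likely drift but does not remove it. Season follows the calendar rather than visit number, and habituation can continue past the first night.

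**The covariate list is open.** It is introduced as a set of examples, and the overall analysis plan foresees covariates that raise the chance of detecting effects. Session could enter that way, so the plan does not rule it out. But that route is optional and conditional on degrees of freedom, whereas session is a factor of the design.

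**Some schemes need no correction.** With one Williams labelling and a subject-by-distribution error term, linear drift neither inflates the SE nor shifts the on/off estimate among completers. True, but the plan names neither the scheme nor the error term.

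**A stronger reading.** A reader might infer that 20% attrition lets drift bias the on/off estimate, or that false positives rise. The documents do not support either. Random loss gives zero mean bias, the test is conservative under the assumed drifts, and nothing suggests that dropout depends on condition or order.

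**Conclusion.** The concern holds as a minor point of efficiency and robustness. The design controls session order, the pre-specified model leaves it out, and any drift then widens the reported SE unless the scheme and error term happen to cancel it. Against an expected main effect of about 12 points, losses of this size are unlikely to change the conclusion. They could matter more for the MPOD interactions, if those effects are smaller, but that was not computed. The SE figures rest on the assumed SD of 10 points and linear drift, and the chance-imbalance figure on all 24 orders being used equally. The omission of the session term does not rest on any assumption.

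**What to change.** In the Aims 1, 2 text, pre-specify session number (1-4, the active sessions) as a categorical within-subjects fixed effect in the mixed model. It should be fitted as a linear mixed model with one record per session, which the plan's allowance for unequal numbers of observations already implies. In the same place, name the counter-balancing scheme and the error term for the distribution effect, and report completers by sequence.

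Cost: 3 degrees of freedom, a sentence or two of analysis text, and under 0.5% in SE if there is no drift. No visit, condition or sample size changes.

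Counter-balancing within each MPOD × diagnosis cell is an optional further step. It would protect order balance where the interactions are estimated, but it changes allocation and no calculation here supports it, so it should be weighed separately.

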Lighting apparatus: The on-axis and off-axis lighting interventions will be delivered via RGB color-tunable LED luminaires (model G2, Ketra, Austin, TX), each driven by a satellite link controller (model N3, Ketra) with a touchpad interface (model X1, Ketra) and housed in fixtures that will be placed directly on desks at which

[figure not shown]

Fig. 4. The layout of the desktop luminaires with respect to the participants' eyes during the experiment (left), and the luminaires' configuration when delivering the on-axis and off-axis interventions (right). The circle shown in the center of the luminaires represents a low-power LED that will be used as a simple on-axis visual task to maintain participants line of sight.

the participants will be seated. The luminaires will be covered by spectrally neutral diffusers to eliminate potential glare. The intervention stimulus will be calibrated using a tripod-mounted illuminance meter (Model X-91, Gigahertz-Optik, [name]). The target photometric characteristics of the intervention light stimulus for measures of illuminance, CL_A, and CS following [name] and [name] ⁷⁰, and equivalent melanopic lux (EML) following Enezi, et al. ⁷¹ are shown in Table 1. To ensure consistency of the delivered lighting dose, participants will be required to use a chin rest, optimally adjusted to maintain a fixed distance of 30 in. from the 22 in. x 5 in. (w x h) light-emitting area of the desktop luminaire (Fig. 4). The on-axis intervention will provide an image $\pm 5^\circ$ in width at each participant's eyes. The off-axis intervention will provide an image $\pm 8-20^\circ$ in width at each participant's eyes.

Table 1. Photometric characteristics of the target blue light and green light stimulus calculated following [name] and [name] ⁷⁰ (CS) and Enezi, et al. ⁷¹ (EML)

Experimental condition	Photopic illuminance (lux)	CL _A	EML	Predicted CS
Blue on-axis / Blue off-axis	26.7	473.7	154.0	0.40
Green on-axis / Green off-axis	250.0	473.7	274.0	0.40

Participant measurements and field monitoring procedures:

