Melatonin Suppression Protocol: On each study night, participants will be required to arrive at the laboratory at 23:30 and remain in dim light (< 5 lux at the eye) for 30 min, followed by a 60-min exposure to one of the 4 experimental conditions (Fig. 5). To ensure consistency of the light distribution with regard to the participants' line of sight over the course of the 1-h exposure, all participants will perform a simple on-axis visual task that involves responding (using a hand-held tally counter) to a flashing, pre-programmed RGB LED source (generic low-power) suspended in the center of the desktop luminaire (see Fig. 4). The visual task will not be performed on the dim-light control night, when participants will be free to operate their personal electronic devices (i.e., iPads, tablets, cell phones, etc.). However, all displays will be covered with orange-tinted media (Roscolux #21 golden amber, Rosco Laboratories, Stamford, CT, USA) to filter out radiation < 525 nm to prevent participants from receiving circadian-effective light from their self-luminous devices. In a previous study, photometric measurements of the stimulus emitted by similarly filtered electronic displays revealed light lev-

Time (hh:mm)	23:30	24:00	00:30	01:00
Condition	Dim light	On axis (CS = 0.40, 27 lux)		
		Off axis (CS = 0.40, 27 lux)		
Saliva sample		Dim-light (CS < 0.10, < 5 lux)		
			S1	S2
				S3

Fig. 5. Experimental protocol showing the relationship between on-axis and off-axis conditions, and salivary melatonin sample times (S1 [0 min], S2 [30 min], and S3 [60 min]).

els of < 5 lux, which translated to a CS of < 0.001⁷³.

Over the course of each experimental session, 3 saliva samples (S1, S2, S3) will be collected from each participant for melatonin analysis. Saliva samples (1 ml) will be collected using the Salivette system (Sarstedt, Nümbrecht, DE), wherein the participant chews on a plain cotton cylinder for 1-2 min, which is immediately placed in a test tube, centrifuged for 5 min at 1000 g, and frozen (-20 °C). The frozen samples from each session will be assayed in a single batch using melatonin radioimmunoassay kits (Direct Melatonin RIA, ALPCO, Salem, NH, USA).

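### The dim-light reference night omits the fixed-gaze task used on light nights, leaving absolute suppression and the between-person comparisons open to an avoidable bias

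*Combined protocol and SAP*

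**What the plan says.** The Melatonin Suppression Protocol section sets the light-night activity: "all participants will perform a simple on-axis visual task that involves responding (using a hand-held tally counter") to a flashing LED in the centre of the luminaire. Its stated purpose is "To ensure consistency of the light distribution with regard to the participants' line of sight over the course of the 1-h exposure". For the reference night the same section says: "The visual task will not be performed on the dim-light control night, when participants will be free to operate their personal electronic devices".

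The next sentence limits the light from those devices: "all displays will be covered with orange-tinted media", chosen "to filter out radiation < 525 nm to prevent participants from receiving circadian-effective light from their self-luminous devices". It adds that similarly filtered displays in a previous study gave under 5 lux and a CS below 0.001. Under Experimental conditions, "the dim light control will target a CS < 0.1 (< 5 lux of 2700 K light) at the eyes".

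The chin rest is described separately, under Lighting apparatus: "participants will be required to use a chin rest, optimally adjusted to maintain a fixed distance of 30 in" from the luminaire, so that the delivered dose is consistent. Neither section says whether it is used on the dim night.

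Under Data and Statistical Analyses, Aims 1, 2, suppression for each condition is obtained by "comparing melatonin levels collected during the dim-light control week to those at the same time in the experimental" conditions. No formula is given. The suppression values then enter a mixed-model ANOVA with distribution and spectrum within subjects, and MPOD group and cognitive status between subjects. A Pearson correlation of suppression with MPOD across MCI patients and controls follows.

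**The concern.** A reference condition should differ from the test conditions only in the factor under study. Here the dim night also differs in four other ways: the task, the control of gaze, what the participant does for the hour, and exposure to the task LED, whose light output is not stated. If any of these affects melatonin, the effect enters every suppression value as though the luminaire had caused it.

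The tests most exposed are those that compare people. MPOD group, cognitive status and the MPOD correlation all rest on each person's level of suppression, and that level moves with the person's own reference. How people spend a free hour with their devices could plausibly differ between MCI participants and controls, although the documents neither say so nor measure it. A difference in control-night behaviour would then look like a difference in light sensitivity. The plan also expects lower MPOD in MCI, so a shift linked to cognitive status could carry into the pooled MPOD correlation.

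The analysis section does not deal with this. Its example covariates are retinal illuminance, gender, season and medication load. No log of device use or dim-night activity is described. The actigraph is worn throughout, but its stated use is to estimate sleep and wake, and it would not show task, gaze or device use.

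**Working it through.** The plan states no figure for this effect, so there is none to reproduce. The calculation shows which quantities move and by how much under stated assumptions.

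**Inputs**
- On/off-axis difference: about 12%, from Anticipated Outcomes, read here as 12 percentage points.
- Illustrative true suppressions: 0.40 on-axis and 0.28 off-axis. The levels are assumptions; only the gap of 0.12 comes from the plan.
- Suppression formula: assumed to be the usual ratio, S = 1 − M_light / M_dim.
- Reference shift b: the proportional change in dim-night melatonin because activity is not matched. It is assumed to lie between −20% and +20%; the documents give no value.

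**Formulas**
- Observed suppression: S_obs = 1 − (1 − S)/(1 + b).
- Observed on/off difference: (S_on − S_off)/(1 + b).

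| b | On-axis (true 0.40) | Off-axis (true 0.28) | On minus off (true 0.12) |
|---|---|---|---|
| −20% | 0.250 | 0.100 | 0.150 |
| −10% | 0.333 | 0.200 | 0.133 |
| −5% | 0.368 | 0.242 | 0.126 |
| 0 | 0.400 | 0.280 | 0.120 |
| +5% | 0.429 | 0.314 | 0.114 |
| +10% | 0.455 | 0.345 | 0.109 |
| +20% | 0.500 | 0.400 | 0.100 |

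For example, at b = +10%, 1 − 0.60/1.10 = 0.455; at b = −10%, 1 − 0.60/0.90 = 0.333.

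**Within-person contrasts.** The four light conditions share one reference per person, so b only divides the contrast by (1 + b). A true zero stays zero and the sign cannot change. In a simulation with 19 participants, an assumed SD of 0.14 for the paired difference, and b varying between people with SD 0, 0.1 or 0.2, the two-sided type I error was 0.048 to 0.051. If suppression were a plain difference, M_dim − M_light, the reference would cancel from the contrast altogether.

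**Between-person comparisons.** All four values of one person move together, so the person's mean moves too. Suppose two groups have the same true suppression and b applies to one group only:
- True 0.40, b = +10%: 0.455 − 0.400 = 0.055.
- True 0.40, b = −10%: 0.333 − 0.400 = −0.067.
- True 0.34 (midpoint of 0.40 and 0.28), b = +10%: (1 − 0.66/1.10) − 0.34 = 0.060.

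The false group difference is therefore about 5 to 7 points.

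**Group by distribution interaction.** With b = +10% in one group only, the on/off difference reads 0.109 in that group and 0.120 in the other, a spurious interaction of about 1 point.

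**The case against.** The strongest defence is that the task exists to hold the line of sight to the luminaire, and with no luminaire stimulus there is no distribution to hold constant. Light from devices, the most obvious route to melatonin, is handled by design: the cited filtered-display values are compatible with the dim-light target. The main Aim 1 hypothesis is a within-person contrast, and neither Aim 1 nor Aim 2 states a hypothesis that MCI participants and controls differ in suppression. Greater light sensitivity in MCI appears only as an exploratory hypothesis in the background. No passage suggests that device behaviour differs by cognitive status or MPOD.

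Most of this stands, and it rules out several stronger readings that a reader might infer:
- That device light contaminates the reference. The amber filters and the CS figure below 0.001 answer this.
- That the chin rest is dropped on the dim night. Only the task is said to be dropped; chin-rest use and posture that night are simply not described.
- That the on/off-axis or blue/green test is biased away from its null. Both share the reference and are at most rescaled.
- That the 5 to 7 points amount to about half of the effect the plan expects. The plan's 12% is a within-person on/off difference and is not a benchmark for a between-group shift.

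What the defence leaves unanswered is that cognitive status and MPOD group are still tested as between-subject factors, and the MPOD correlation is the stated hypothesis of Aim 2. These have no protection from a shared reference. Nor does the purpose of the task explain why the reference hour should be left free, when the same seat and time slot are available.

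**Conclusion.** The mismatch is real and avoidable, but limited. The reference night differs from the light nights in task, gaze, activity and task-LED exposure. Absolute suppression is affected if any of these alters melatonin. The tests on MPOD group, cognitive status and the MPOD correlation are biased only if the alteration also differs with group or MPOD.

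The size cannot be taken from the documents. The figure of 5 to 7 points rests on three assumptions: a ratio formula, a true suppression of 40%, and a 10% shift confined to one group. It illustrates sensitivity and does not estimate a bias that is known to occur. This is a cheap improvement to the design and does not undermine the main within-person comparison.

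**What to change.** In the Melatonin Suppression Protocol section, run the same seated task on the dim-light night with the same chin rest and flashing LED, the luminaire stimulus off, and no personal devices during the 60 minutes. Because the LED's output is not given, measure total light at the eye with the LED running and confirm that it stays within the plan's own limit of under 5 lux. In the Aims 1, 2 analysis text, state the suppression formula.

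If the task cannot be matched, the lesser step is to state the dim-night seating and chin-rest procedure and to record device use, so that it can at least be compared between groups.

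The equipment and the time slot are already in place. The cost is one more hour of a tedious task per participant. The change does not remove a separate difference: the dim night is always run first, while only the four light conditions are counter-balanced.
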